7.2.2.3. Dose-Escalation Method

For Part A, the proposed starting dose level will be 0.2 mg/kg. Dose escalation will proceed at a maximum dose increment of 100%. An accelerated dose-escalation scheme will be used, as follows: initial cohorts will enroll at least one patient each until a dose level of 1.6 mg/kg is reached, unless a \geq Grade 2 toxicity that is at least possibly related to LY3076226 is observed requiring additional patients to be enrolled to a dose level. After which a modified 3+3 scheme, with incorporation of a Bayesian model-based, toxicity-band method (Neuenschwander et al. 2008), will be followed, wherein at least 3 patients will be enrolled in each of the subsequent cohorts. The Bayesian model-based, toxicity-band method incorporates the prior expectations of the dose-toxicity curve and the observed DLT data after each cohort and provides quantitative guidance on the determination of the dose level for the next cohort, with control of overdosing probability. This method will be applied to the observed data on an ongoing basis throughout the dose escalation. The toxicity-band method will stop if the prespecified maximum number of patients is reached or the recommended next dose level has been administered to at least 6 patients.

During the dose-escalation period, the investigators and Lilly CRP/CRS will consider both the model recommendation and the observed DLT rate at each cohort to determine the next dose level and determine when to stop dose escalation. Safety data, in particular, AEs, will be the primary criteria for dose escalation. In addition, if available at the time of the dose-escalation decision, PK (C_{max} , AUC, and systemic clearance [CL]) results will be used as secondary/supporting data for dose escalation. Additional patients may, therefore, be enrolled at a specific dose level to characterize PK/PD. No dose escalation can occur without prior discussion and agreement between the investigator and the Lilly CRP/CRS; the decision will be documented in writing. Inpatient dose escalations are not permitted.

The example dose levels for Part A are shown in [Table JOBA.3](#). Intermediate or higher dose levels may be explored, if deemed necessary, after discussion between the Lilly CRP/CRS and investigators. The toxicity-band method has the ability to accommodate additional dose levels naturally.

Details regarding the toxicity-band method for this study are provided in [Attachment 10](#).

If, during dose escalation, a situation presents itself that is not described above, Lilly CRP/CRS and investigators will determine the best method to select the appropriate dose for the patient(s) involved, using all available information. The decision will be documented in writing. No dose escalation can occur without prior discussion and agreement between the site-specific investigator and the Lilly CRP/CRS. Written notification will be sent to the site specifying the dose to be used for each patient at each dose level.

Table JOBA.3. Example of LY3076226 Dose Levels for Part A

Cohort	LY3076226 Dose Level (mg/kg)
1	0.2
2	0.4
3	0.8
4	1.6
5	2.4
6	3.2
7	4.0
8	5.0

Based on the ongoing safety reviews, modifications to the dose-escalation strategy or other design elements may be made via protocol amendment to ensure patient safety.

7.2.3. Dose Confirmation in Patients with Known Alterations of FGFR3 (Parts B and C)

Once the MTD has been defined in Part A, Parts B (urothelial carcinoma) and C (other malignancies) will be activated and will enroll up to approximately 15 patients who have known alterations of FGFR3, to further define the safety and tolerability of LY3076226 and to characterize the exploratory biomarker assays. The dose of LY3076226 in Parts B and C will not exceed the MTD of LY3076226, as defined during dose escalation in Part A. The exact sample size of this cohort will be dependent on the number of patients who have known FGFR3 alterations treated at the MTD during dose escalation in Part A, and will be adjusted so that a total of approximately 15 patients will be treated.

If a DLT-equivalent toxicity occurs in one third or more of patients during Cycle 1 (with a minimum of 6 patients enrolled), the enrollment of new patients will cease until the Lilly CRP/CRS and investigators assess the severity and nature of the toxicities. A data review will be performed to determine whether to continue at the current LY3076226 dose or whether the dose of LY3076226 should be reduced. The toxicity-band method used in the dose-escalation phase will be updated with the additional data observed in Parts B and C to confirm the MTD selection and/or to inform any need to further refine the MTD. This decision will be documented in writing.

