7.2.2. Dose Escalation

7.2.2.1. Dose-Limiting Toxicity Determination and Maximum Tolerated Dose Definition

Dose-limiting toxicity (DLT) is defined as an AE occurring during Cycle 1 that is at least possibly related to LY3076226 and fulfills any one of the following criteria using the NCI-CTCAE v 4.0:

- CTCAE Grade ≥ 3 non-hematological toxicity. Exceptions will be made for the following:
 - Nausea, vomiting, diarrhea, and constipation that can be controlled with treatment (Grade 3 and Grade 4 nausea, vomiting, or diarrhea should be considered DLTs if persisting for more than 48 hours, despite supportive intervention.)
 - Anorexia
 - Grade 3 fatigue lasting ≤ 5 days
- Grade 3 elevations of ALT and/or AST lasting >7 days.
- Concurrent elevation of ALT $>3 \times$ ULN and total bilirubin $>2 \times$ ULN in the absence of biliary obstruction or other causes that could reasonably explain the elevation.
- CTCAE Grade 4 neutropenia of >7 days' duration
- Any febrile neutropenia
- CTCAE Grade 3 thrombocytopenia with bleeding
- CTCAE Grade 4 thrombocytopenia with or without bleeding
- Any other significant toxicity deemed by the primary investigator and Lilly clinical research personnel to be dose limiting (for example, any toxicity that is at least possibly related to the study medication and that requires the withdrawal of the patient from the study during Cycle 1 or delays the start of Cycle 2 by >14 days).

For the purpose of this study, the MTD is defined as the highest dose tested that has less than 33% probability of causing a DLT.

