7.2.2.2. DLT-Equivalent Toxicity

A DLT-equivalent toxicity is defined as an AE occurring during Cycle 2 and beyond that would have met the criteria for a DLT if it had occurred during Cycle 1. For individual patients experiencing a DLT-equivalent toxicity, dose adjustments will be made as outlined in Section 7.2.6. At each interim analysis (as defined in Section 10.10), the rate of DLT-equivalent toxicities will be assessed. If the rate of DLT-equivalent toxicities is unacceptable (for example, a DLT-equivalent toxicity is observed in $>33\%$ patients at a given dose level), the data will be reviewed by study investigators and the Lilly CRP/clinical research scientist (CRS) and a safety analysis may be triggered. If the findings indicate that a dose level does not have an acceptable safety profile for chronic (Cycle 2 or later) administration, then a lower dose level will be chosen for further investigation. This decision will be documented in writing.

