8.1.4. Safety Monitoring

The Lilly CRP/CRS will monitor safety data throughout the course of the study.

Representatives from Lilly Global Patient Safety will specifically monitor SAEs. Lilly will review SAEs within time frames mandated by company standard operating procedures.

Ophthalmologist may perform additional examinations when visual changes or other ocular symptoms occur, at their discretion as clinically indicated.

Details for hepatic monitoring depend upon the severity and persistence of observed laboratory test abnormalities. Potential for biliary obstruction should be assessed. To ensure patient safety and comply with regulatory guidance, the investigator is to consult with the Lilly CRP/CRS regarding collection of specific recommended clinical information and follow-up laboratory tests (see [Attachment 3](#)). If a study patient experiences concurrent elevated ALT $>3 \times$ ULN and elevated total bilirubin $>2 \times$ ULN, clinical and laboratory monitoring should be initiated by the investigator. If this is determined to be in the absence of biliary obstruction or other causes than can reasonably explain the concurrent elevation, then the patient should be discontinued from LY3076226.

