10.10. Interim Analyses

Once the LY3076226 MTD is defined for Part A, an interim analysis will be performed prior to opening Parts B and C.

At the end of Parts B and C, an analysis may be conducted to review available safety, PK, and efficacy data once all evaluable patients have either completed 3 cycles of study treatment or discontinued from the study treatment.

Because this is a dose-finding study, data will be reviewed on a cohort-by-cohort basis during the study, until the MTD is determined for Part A. The purpose of these cohort-by-cohort reviews is to evaluate the safety data and any available PK data at each dose level and determine if a DLT has been observed that would suggest MTD has been met or exceeded. The investigators and the Lilly study team will make the determination regarding dose escalation based upon their review of the safety and tolerability data as described in this protocol.

In Parts B and C, if a DLT-equivalent toxicity occurs in one third or more of patients during Cycle 1 (with a minimum of 6 patients enrolled), a data review will be performed to determine whether to continue at the current LY3076226 dose or whether the dose of LY3076226 should be reduced. Refer to Section [7.2.3](#) for more details.

If an unplanned interim analysis is deemed necessary, the sponsor will determine if it is necessary to amend the protocol.

11. Informed Consent, Ethical Review, and Regulatory Considerations

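### The Parts B/C enrolment pause counts DLT-equivalent toxicities in Cycle 1, but the protocol defines that term as Cycle 2 onward, so as written the rule can count no event

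*Protocol*

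**What the plan says.** The protocol defines two toxicity terms by time window. Section 7.2.2.1: "Dose-limiting toxicity (DLT) is defined as an AE occurring during Cycle 1 that is at least possibly related to LY3076226". Section 7.2.2.2: "A DLT-equivalent toxicity is defined as an AE occurring during Cycle 2 and beyond", with the further condition that the event would have been a DLT had it fallen in Cycle 1. The toxicity criteria are the same; only the window differs.

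The expansion rule is in Section 7.2.3: "If a DLT-equivalent toxicity occurs in one third or more of patients during Cycle 1 (with a minimum of 6 patients enrolled". When it is met, enrolment of new patients stops until the sponsor's clinical staff and the investigators have assessed the toxicities, and a data review decides whether to keep or reduce the dose. Section 10.10 repeats the condition as the trigger for that review: "In Parts B and C, if a DLT-equivalent toxicity occurs in one third or more of patients during Cycle 1". SAP 6.15 carries the same wording. SAP 6.8.2 introduces another label, dose-equivalent toxicities, with no time window.

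Parts B and C each enrol up to approximately 15 patients at a dose not above the MTD (Sections 6.2 and 7.2.3). The recommended Phase 2 dose is set after both are complete (Section 7.2.4).

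**The concern.** The rule names one kind of event and requires it in a window that the event's own definition excludes. A reader who applies the definitions finds nothing to count. A reader who tries to repair the sentence has two options: treat the event as a DLT and keep Cycle 1, or keep the DLT-equivalent term and drop the Cycle 1 restriction. These give different numerators and different times at which enrolment would stop. The first is much the more natural, but the text does not choose it.

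This matters because the sentence is the automatic brake on enrolment in a Phase 1 study of a cytotoxic conjugate, in the cohorts whose safety data feed the recommended Phase 2 dose, which is the primary objective. If the trigger does not work, the decision to pause depends on someone raising the question or on every reader inferring the same intent.

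**Working it through.** Neither document states an operating characteristic for this rule, so there is no figure to reproduce. The check compares the definitions, looks for any other rule that would do the same job, and then illustrates what a working rule would do.

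**1. Time windows**

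| Place | Event | Window |
|---|---|---|
| Protocol 7.2.2.1 | DLT | Cycle 1 |
| Protocol 7.2.2.2 | DLT-equivalent toxicity | Cycle 2 and later |
| Protocol 7.2.3 (pause and review) | DLT-equivalent toxicity | Cycle 1 |
| Protocol 10.10 and SAP 6.15 (review) | DLT-equivalent toxicity | Cycle 1 |

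Cycle 1 and Cycle 2 onward have no overlap. The count is therefore always 0, and the literal probability of a pause is 0 at every true toxicity rate. No passage in either document redefines the term for Parts B and C.

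**2. Other safeguards in expansion**

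- Section 7.2.2.2 gives more than 33% at a dose level as an example of an unacceptable rate. "At each interim analysis (as defined in Section 10.10), the rate of DLT-equivalent toxicities will be assessed". It leads to a review and an optional safety analysis, with no stated halt to accrual, and by definition it covers Cycle 2 onward.
- On the timing of those interims, Section 10.10 says: "Once the LY3076226 MTD is defined for Part A, an interim analysis will be performed prior to opening Parts B and C". The later analysis is optional and comes at the end of Parts B and C.
- Section 7.2.3 adds: "The toxicity-band method used in the dose-escalation phase will be updated with the additional data observed in Parts B and C". No schedule or pause threshold is attached.
- Section 8.1.4: "The Lilly CRP/CRS will monitor safety data throughout the course of the study". No threshold is given.
- Sections 7.3 and 7.6.1 presuppose that accrual may stop for toxicity or a DLT, but set no number.

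None of these is a numeric rule that pauses enrolment during expansion.

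**3. Illustration: the rule if it counted Cycle 1 DLTs**

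The threshold is events/n ≥ 1/3 with n ≥ 6, so the smallest triggering counts are 2/6, 3/9, 4/12 and 5/15. The true rates p below are assumed for illustration.

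Single look at 6 patients: P(X ≥ 2) = 1 − (1−p)^6 − 6p(1−p)^5. At p = 0.20 this is 1 − 0.262 − 0.393 = 0.345.

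Checked after every patient from the 6th to the 15th in one Part: let f_n(x) be the probability of x events in n patients without having triggered. Then f_n(x) = (1−p)·f_{n−1}(x) + p·f_{n−1}(x−1). From n = 6, any state with 3x ≥ n is removed and its probability added to the total for firing.

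| Assumed true Cycle 1 rate | 0.10 | 0.20 | 0.33 | 0.40 | 0.50 |
|---|---|---|---|---|---|
| Literal wording | 0 | 0 | 0 | 0 | 0 |
| Single look at n = 6 | 0.114 | 0.345 | 0.642 | 0.767 | 0.891 |
| Every patient, n = 6 to 15 | 0.129 | 0.420 | 0.780 | 0.896 | 0.975 |

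**4. A side point: the counting unit**

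The text does not say whether the one third is taken per Part or across both. If per Part, the probability that at least one of two Parts pauses is 1 − (1 − P15)², where P15 is the last row above. At p = 0.20 this is 1 − 0.58² = 0.66; at p = 0.33 it is 1 − 0.22² = 0.95. Pooled up to 30 patients, the same recursion gives 0.44 and 0.84.

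**The case against.** The strongest reply is that the sentence has only one sensible reading. It carries its own window, threshold and minimum, and the DLT-equivalent definition borrows the DLT criteria unchanged, so reading it as Cycle 1 events meeting those criteria is what gives it effect. Cycle 1 DLTs in Parts B and C will also be identified anyway: the toxicity-band update runs on observed DLT data, and Section 10.4 and SAP 6.8.2 both call for DLT summaries. Even a corrected rule only pauses enrolment until sponsor staff and investigators have assessed the events, so the final decision is theirs in any case.

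Most of this stands. The intent can be inferred, conduct would probably follow it, and what a literal reading loses is the automatic trigger for the pause and review. It is also fair to say that the probabilities describe a corrected rule at assumed rates: they do not measure how likely staff are to read the text literally. The counting-unit question is separate; it would exist whatever term was used, and the conclusion does not rest on it.

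None of this removes the conflict. The defined term excludes the window in which it is to be counted, the wording appears in three places, and the SAP repeats the condition without correcting it. A rule that stops enrolment should not need its meaning reconstructed.

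**Conclusion.** The concern holds. The only numeric rule that pauses expansion enrolment is wrong as written: by the protocol's own definitions it can count no event. This is a statement about the text, not a prediction that toxicity would be missed, since general monitoring and the model update remain and the intended meaning is recoverable. It should be fixed because it is a safety trigger, repeated uncorrected in the SAP.

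The conclusion depends only on the definitions. The illustrative probabilities further assume independent patients, the same rate in both Parts, each Cycle 1 outcome known before the next check, and 15 patients per Part. That last figure is an upper limit, because Section 7.2.3 adjusts the expansion size for patients with FGFR3 alterations already treated at the MTD in Part A.

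**What to change.** In Protocol Sections 7.2.3 and 10.10 and in SAP 6.15, replace *a DLT-equivalent toxicity* with *an AE meeting the DLT criteria of Section 7.2.2.1*. Keep the one-third threshold and the 6-patient minimum. Leave the definition in Section 7.2.2.2 as it is, because it serves the review of toxicity in Cycle 2 and later. While the sentence is open, add a few words saying whether the fraction is counted per Part or pooled across Parts B and C.

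The cost is one phrase in two protocol sections and one SAP section, plus the words on counting. No additional data or patients are needed.

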7.2.4. Recommended Phase 2 Dose (RP2D)

The RP2D will be determined after the completion of Parts B and C. The RP2D will be agreed upon following discussion between the investigators and the Lilly CRP or CRS and will include an assessment of safety, PK, and PD data. This will not exceed the MTD.

7.2.5. Infusion-Related Reactions

Due to the risk of hypersensitivity reactions with any biological agents, all patients should continue to be closely monitored for signs and symptoms indicative of an infusion-related reaction (IRR) both in the acute period (immediately or within 24 hours after dosing) and up to several days to a few weeks after dosing for delayed reactions. Acute assessments should include an assessment of vital signs starting at the time of initiation of the infusion and continuing until at least 60 minutes after the end of the infusion. At a minimum, vital signs should be obtained prior to infusion, during infusion, and at 1 hour post-infusion. The exact frequency of the monitoring is left to the discretion of the investigator. Monitoring should be performed in an area where resuscitation equipment and other agents (for example, epinephrine, corticosteroids) are readily available.

Per the CTCAE v 4.0 definition of IRRs, symptoms occurring during or following infusion of investigational therapy may be defined according to AE categories such as allergic reaction, anaphylaxis, or cytokine release syndrome. In the setting of symptoms occurring during or following infusion of investigational therapy, investigators are encouraged to use the AE term “infusion-related reaction” and any additional terms, including those not listed here, that best describe the event.

Section 7.2.6 provides treatment recommendations for IRRs.

If, at any time, a patient experiences an IRR to LY3076226, all attempts will be made to obtain a blood sample for immunogenicity analysis as close to the onset of the event as possible, at the resolution of the event, and 30 days following the event. A portion of the sample taken for immunogenicity testing may be used for PK analysis, in the setting of IRRs.

If IRRs are observed, premedication with diphenhydramine hydrochloride (or equivalent), dexamethasone (or equivalent), or other medications as medically indicated may be considered for future patients. The decision to implement premedication for drug administration in subsequent patients will be made following a discussion between the investigators and sponsor and will be documented in writing.

7.2.6. Dose Adjustments and Delays

7.2.6.1. General Dose Adjustments and Delays

Once a patient has had a dose reduction (has started a new cycle at the reduced dose), all subsequent infusions will be at the reduced dose level; there will be no resumption to prior dose level(s). Any patient experiencing toxicity that would necessitate more than 2 dose reductions must discontinue treatment.

The following criteria should guide dosing:

- Before the start of each cycle, the following parameters are required:
 - Hematologic: ANC $\geq 1.5 \times 10^9/L$, platelets $\geq 100 \times 10^9/L$, and hemoglobin ≥ 8 g/dL. (In Part C only, patients with multiple myeloma are allowed the following: ANC $\geq 1.0 \times 10^9/L$, platelets $\geq 50 \times 10^9/L$, and hemoglobin ≥ 8 g/dL.)
 - Non-hematologic: AEs must resolve to CTCAE v 4.0 Grade ≤ 1 or baseline. Exceptions will be made for: alopecia, fatigue, or other toxicities that can be controlled with standard treatment; these toxicities must resolve to Grade ≤ 2 .
- If subsequent cycles are delayed by more than 14 days due to an AE that is at least possibly related to LY3076226, the patient should be removed from study drug treatment and should complete subsequent follow-up.
- If the patient is in Cycle 3 or beyond and is continuing to receive benefit from therapy, delays of greater than 14 days may be acceptable if agreed upon by both the investigator and sponsor. For instance, if a patient has a non-drug-related AE such as prolonged flu, the patient may continue on therapy if, in the opinion of the investigator, he/she is showing benefit from therapy and has recovered sufficiently from the AE.
- A delay of no more than 7 days because of holidays, weekends, inclement weather, or other justifiable events will be permitted and will not be counted as a protocol deviation.

Table JOBA.4 presents LY3076226 dosing guidelines for managing AEs of concern, which may or may not be associated with LY3076226 therapy.

Table JOBA.4. LY3076226 Dosing Guidelines for Managing Adverse Events of Concern for Study I7O-MC-JOBA

Event and Grade	Specifics	LY3076226 Dosing Guidelines, Including Dose Reductions and Delays
Infusion-Related Reactions		
Grade 1	First occurrence	Decrease LY3076226 infusion rate by 50% and monitor closely for any worsening. For subsequent infusions, premedicate with diphenhydramine hydrochloride; additional premedication may be administered at the investigator's discretion.
Grade 2	First occurrence	Stop LY3076226 infusion. Administer diphenhydramine hydrochloride and acetaminophen for fever. Supply oxygen. Resume infusion at 50% of previous rate once the infusion-related reaction has resolved or decreased to Grade 1 in severity, and monitor closely for any worsening. For subsequent infusions, premedicate with diphenhydramine hydrochloride; additional premedication may be administered at the investigator's discretion. The reduced rate should be used for all subsequent infusions.
Grade 1 or 2	Second occurrence	Administer dexamethasone.
Grade ≥ 3		Stop LY3076226 infusion and disconnect infusion tubing from the patient. Administer diphenhydramine hydrochloride, dexamethasone, bronchodilators for bronchospasm, and other medications/treatment as medically indicated. Patients must not receive any further LY3076226 treatment.
Other Toxicities		
Grade ≥ 3	First occurrence	Delay LY3076226 treatment until Grade ≤ 1 or baseline following the rules in Section 7.2.6.1. Based on the investigator's discretion, the full dose of LY3076226 may be administered or the dose may be reduced to the next lowest dose level. If the event recurs at the same grade, then dose reduce LY3076226 to the next lowest dose level.
Grade ≥ 3	Second occurrence	Delay LY3076226 treatment until Grade ≤ 1 or baseline following the rules in Section 7.2.6.1. Dose reduce LY3076226 to the next lowest dose level.

